Pregnant women are a priority group for the receipt of the seasonal inactivated influenza vaccine because of: i) the increased risk of adverse outcomes to themselves and their fetuses should they become ill with influenza, and ii) the need to protect infants during a period when they are too young to receive the vaccine themselves. Although the seasonal inactivated influenza vaccine has been shown to be safe and well tolerated in the second and third trimesters of pregnancy, little data exist on the outcomes of vaccination during the first weeks of pregnancy. If adverse outcomes occur, then this may be tied to hormonal changes that are secondary to inflammatory cytokine responses following vaccination. During a healthy pregnancy, steroid hormones, including estradiol, progesterone, and cortisol increase substantially and contribute to reductions in inflammatory cytokine concentrations that are necessary to support a successful pregnancy [1-3]. Through the mechanisms of bidirectional communication between endocrine and immune cells, questions arise as to whether activation of immune cells by infection or vaccination and the subsequent production of inflammatory cytokines, including TNF- α , could change steroid hormone concentrations and the outcome of pregnancy [4]. This open label prospective trial expands our pilot study conducted during the 2013-2014 influenza season in which we examined the effect of seasonal inactivated influenza vaccine (IIV) on inflammatory cytokines and hormonal responses in healthy women of reproductive age. Our initial findings showed a non-significant 20% decrease in serum progesterone vaccination as compared to the same menstrual cycle time point (day 17) in the non-vaccinated month[5]. Initial findings also showed increases in some cytokine levels after vaccination [5]. With the additional participants provided by this amendment, we would like to repeat our initial pilot study during 1 or 2 additional influenza seasons with some modifications, in order to better understand the early responses to influenza vaccine and the effects on hormones. The women will be recruited at the Center for Immunization Research, Johns Hopkins Bloomberg School of Public Health, followed for one menstrual cycle to measure estradiol, progesterone, and cytokines and then vaccinated with the seasonal inactivated influenza vaccine prior to ovulation during a second month. At the investigator's discretion, or if there is active circulation of influenza virus in Baltimore, we will vaccinate during the first menstrual cycle (prior to ovulation) and then follow for a second menstrual cycle for comparison. After vaccination, they will be followed for cytokine and chemokine responses as well as changes in the concentrations of estradiol and progesterone hormones.

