Despite the decreases seen in IL-8 in non-pregnant adult men and women, two recent studies looking at inflammatory responses in pregnant women after influenza vaccination showed an increase in concentrations of IL-8, CRP, IL-6, TNF α , and MIF 48 hours after influenza vaccination [12, 13]. Discrepancies among studies might be caused by whether studies recruited women only [12, 13] or combined outcome data from both women and men [23]. No group has looked to see if these inflammatory responses after vaccination affect steroid hormone levels or if they have any effect on the earliest stages of pregnancy. This study is designed to explore these questions.

During our initial pilot study conducted during the 2013-2014 influenza season we examined the earliest immune responses to influenza vaccine and the potential impact on reproductive and stress hormones on women of reproductive age. Our initial findings showed no significant changes in serum hormone levels of estrogen, progesterone and cortisol after vaccination, compared with similar time points in a baseline menstrual cycle without vaccination. However, a non-significant 20% decrease in serum progesterone was observed after vaccination as compared to the non-vaccinated month[5]. Initial findings also showed increases in some cytokine levels after vaccination, compared with levels before vaccination during the vaccination menstrual cycle; cytokine levels were not assessed during the baseline menstrual cycle without vaccination[5]. Studying a larger number of women over 1 or 2 additional influenza seasons would help us better understand the effects of IIV on early immune responses and hormone levels.

III. Study Design:

A.

This is an open label study looking at the effect of influenza vaccine on cytokines and reproductive hormones. We will recruit women of reproductive age who are not on hormonal birth control, measure their cytokines and reproductive hormones for 1 month to establish a baseline, and then vaccinate them with the seasonal inactivated influenza vaccine just prior to ovulation, and follow the cytokines and reproductive hormones for the remainder of their cycle. We will use commercially available urine Luteinizing hormone (LH) strips to measure ovulation.

B. Provide a sample size and a justification as to how you arrived at that number. If you use screening procedures to arrive at a final sample a table may be helpful.

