- a. Provide sample size and a clear justification as to how you arrived at your projected sample size. We will evaluate the effect of vaccine on 90 women (see below; this includes the 30 women enrolled in the pilot study). Women who drop out before completing data collection for two menstrual cycles will be replaced. We may need to enroll up to 120 women in order to ensure a complete data set.

V. Study Procedures:

In this section, provide details of your procedures, particularly as they relate to human subjects. If this is a multi-center study, make the role of JHSPH clear. If the JHSPH will serve as **data coordinating center**, indicate in the sections below which procedures JHSPH will not be performing. Additional information regarding data coordinating centers is requested in a later section. If your study will develop in phases, address each item below by phase.

A. **Recruitment Process:**

1. Describe how you will identify, approach, and inform potential participants about your study. Include details about who will perform these activities and what their qualifications are.

IRB-approved recruitment information will be posted and distributed throughout the campuses of the Johns Hopkins University, including the Schools of Public Health, Medicine and Nursing as well as other locations as allowed in the greater Baltimore area. In addition, the CIR has ongoing recruitment using IRB-approved advertising (electronic and/or other media publications and advertising), social media, an IRB-approved screening protocol (H.22.02.04.19. A2), and a large data base of former CIR clinical trial participants and initial contacts that we can query for potential recruits.

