The skewness of the cytokine concentration distributions will be checked using Kolmogorov-Smirnov test of normality. Transformation of the non-normal data to achieve normality will be attempted using natural logarithms. In the event that natural logarithm transformation fails to normalize the data then non-parametric tests will be used. Relationships between the different inflammatory biomarkers interest will be analyzed using Pearson's correlation or with Spearman's rank test, as needed. The mean difference (SD) in cytokine concentrations between baseline and at 24 hours post-vaccination, and between baseline and 48 hours post-vaccination within individuals will be evaluated by paired t-test for parametric data or by the Wilcoxon matched-pairs signed rank sum test for non-parametric data. Stratified analyses will be used to determine if host characteristics

modify the effects of vaccination on hormonal responses. Our study design will also allow us to look at differences in cytokines at various points in the nonvaccination menstrual cycle.

EA2: To determine if post-vaccination inflammatory biomarker responses to IIV receipt (days 40 and 41) are associated with changes in reproductive hormone levels during the second menstrual cycle.

-H3: Changes in serum pro-inflammatory responses between baseline and 24(and/or 48)-hours post-vaccination, will be inversely correlated with serum reproductive hormone concentrations during the second menstrual cycle.

Correlations between changes in post-vaccination serum pro-inflammatory biomarkers (days 39 to 40, 39 to 41) and changes in serum hormone responses during the second menstrual cycle (days 45 to 49, 45 to 56), will be calculated using Pearson's correlation coefficient and evaluated using the paired t-test for parametric data or Spearman's rank correlation test and the Wilcoxon matched-pairs signed rank sum test for non-parametric data. In addition, we will correlate changes in the hormone levels observed in the second cycle to the first cycle (days 17 to 21, 17 to 28) using the same analytical techniques.

EA4: To describe the frequency of adverse events in the 7 days after vaccination, including fever, myalgia, malaise, and hypersensitivity reactions, and to determine if these adverse events are associated with cytokines responses.

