-H4: Adverse events, specifically fever, myalgia and malaise after vaccination, are associated with a greater inflammatory cytokine response than seen in people who do not experience these events.

The frequency and proportion of participants who experience vaccine-associated adverse symptoms will be reported. In addition, differences in mean (SD) serum inflammatory biomarker concentrations at 24 and 48 post-vaccination and mean (SD) changes in serum concentrations following vaccination by adverse symptom status will be explored using t-tests.

5. **Answer the following if they are relevant to your study design:**

A. If the study has different arms, explain the process for assigning participants (intervention/control, case/control), including the sequence and timing of the assignment.

Subjects will be screened for eligibility based on their age, medical, vaccination and menstrual history, and birth control methods used. All participants will receive the same influenza vaccine. We will aim to enroll equal numbers of women who have received an H1N1 containing vaccine with influenza vaccine naïve women. This will allow us to compare responses of women with previous vaccination with those without prior history of vaccine.

B. If human biospecimens (blood, urine, saliva, etc.) will be collected, provide details about who will collect the specimen, the volume (ml) and frequency of collection, how the specimen will be used, stored, identified, and disposed of when the study is over. If specimens will be collected for use in future research (beyond this study), complete the "Biospecimen Repository" section below.

Specimens will be collected by the PI, nurses and staff trained in the proper collection of samples and blood draws. Serum specimens will be collected during this study. Any remaining specimens at the conclusion of the study will be retained under the CIR biorepository protocol (CIR 213 IRB Number R.22.05.04.29.A2.)

- C. If genetic/genomic analyses are planned, address whether the data will be contributed to a GWAS or other large dataset. Address returning unanticipated incidental genetic findings to study participants.

N/A

- D. If clinical or laboratory work will be performed at JHU/JHH, provide the JH Biosafety Registration Number.

N/A

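### EA2, EA4 and the prior-vaccination comparison combine women from two or three influenza seasons with no season term; adding one is a cheap improvement to exploratory analyses

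*Protocol*

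**What the plan says.** **Who is analysed.** Protocol Section II describes an "initial pilot study conducted during the 2013-2014 influenza season". The opening summary plans to "repeat our initial pilot study during 1 or 2 additional influenza seasons with some modifications". Section III.B gives 30 women a year and 90 in total, and Section IV item a confirms that "this includes the 30 women enrolled in the pilot study". Section III.B describes the pilot women as student enrollees; Section IV recruits from the university campuses and the surrounding community.

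**What is already measured.** Section II reports pilot results: "Initial findings also showed increases in some cytokine levels after vaccination". The pilot hormone results supply the inputs to the power calculation.

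**How the between-women questions are analysed** (Section V, Study Implementation, items 4 and 5.A).
- EA2 begins "Correlations between changes in post-vaccination serum pro-inflammatory biomarkers (days 39 to 40, 39 to 41" and relates these to within-cycle hormone changes by Pearson or Spearman correlation.
- EA4 compares 24 h and 48 h biomarker concentrations, and their changes, "by adverse symptom status will be explored using t-tests".
- Item 5.A says "All participants will receive the same influenza vaccine" and intends a comparison of women with and without prior vaccination, enrolled in equal numbers. It states no test.

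Stratified analyses are by host characteristics only. The SAP holds only the power calculation. Neither document mentions season as a factor, an assay-batch rule, or re-assay of pilot samples.

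**The concern.** When each woman is compared with herself, whatever is common to her season largely cancels. A correlation or group comparison across women has no such protection. Season here stands for several things that may change together: the seasonal vaccine, assay timing, study procedures and perhaps the source population.

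If both variables in EA2 differ by season, the pooled correlation mixes a between-season component into the within-season one. It can then show a link that no season shows, or hide one that every season shows. The same holds for EA4 and the prior-vaccination comparison if both the biomarker and the group's share of women differ by season. If only one of the two differs, the cost is precision.

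H3 in EA2 is the proposed mechanism from vaccine inflammation to hormone change, and the plan applies p < 0.05 to all analyses.

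**Working it through.** **The plan's own figure.** The only power figures concern the paired progesterone comparison. For ratio 0.70 and correlation 0.60, the SD of the difference is √(0.51² + 0.54² − 2×0.60×0.51×0.54) = 0.470 and the effect is log10(0.70) = −0.155. A two-sided paired t-test with n = 90 then has power 0.87, against 0.86 stated. This is a within-woman comparison, so the point does not touch it. No figure is given for EA2, EA4 or the prior-vaccination comparison.

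**EA2, set-up.** Take 30 pilot and 60 later women (Section III.B). Assume that the later women differ from the pilot by *a* in biomarker change and *b* in hormone change, in within-season SDs, and that the within-season correlation is ρ. The between-season covariance is (1/3)(2/3)ab = 2ab/9, so the pooled correlation is about

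(ρ + 2ab/9) / √[(1 + 2a²/9)(1 + 2b²/9)].

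Rejection rates are from simulation (20,000 or more runs, Pearson, two-sided 0.05; 88 degrees of freedom pooled, 86 adjusted for three seasons).

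| a | b | ρ | pooled r | pooled rejects | adjusted rejects |
|---|---|---|---|---|---|
| 0 | 0 | 0 | 0 | 5% | 5% |
| 1 | 0 | 0 | 0 | 5% | 5% |
| 0.5 | 0.5 | 0 | 0.0556/1.0556 = 0.053 | about 8% | 5% |
| 1 | 0.25 | 0 | 0.0556/√(1.2222×1.0139) = 0.050 | about 8% | 5% |
| 0.75 | 0.75 | 0 | 0.125/1.125 = 0.111 | 17% | 5% |
| 1 | 1 | 0 | 0.2222/1.2222 = 0.182 | 41% | 5% |
| 0 | 0 | −0.30 | −0.300 | 83% | 82% |
| 0.5 | 0.5 | −0.30 | −0.2444/1.0556 = −0.232 | about 60% | 82% |
| 1 | 0 | −0.30 | −0.30/√1.2222 = −0.271 | 74% | 82% |

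Same-direction shifts produce a false positive correlation and hide a true inverse one. Opposite shifts give the same false-positive rates with a negative sign, which is the direction H3 predicts.

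**EA4.** Assume symptoms in 10% of pilot and 30% of later women (3 + 18 = 21 affected) and a 1 SD level shift. The t-test is then falsely positive in 13.5% of trials, against about 5% with a season term. With 20% and 30% it is about 7%. Section VII.B of the Protocol, however, expects myalgia/malaise in about 2%, or 0.02 × 90 = 1.8 women. At 2% in every season the false-positive rate is about 5%. The chance of fewer than two affected women is 0.98⁹⁰ + 90×0.02×0.98⁸⁹ = 0.162 + 0.298 = 0.46. No rate for fever is given.

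**Prior vaccination.** Assume biomarker level rises by 0.5 SD from each season to the next. If half of the women were previously vaccinated in every season, a pooled t-test keeps 5% error, and power for a true 0.6 SD difference falls from 0.80 to 0.74 (adjusted 0.79). If the share is 30%, 50% and 70%, pooled false positives are 22% and adjusted 5%. If it is 70%, 50% and 30% with a true 0.6 SD difference, pooled power is 0.30 and adjusted 0.74.

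**The case against.** The best case for the plan has five parts.

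- **The same-vaccine sentence.** A reader might infer that it is false, or that it is an analysis assumption. The documents do not support that. It answers a form item about arms and says that there are none. Item 5.F.c of the same section says that everyone gets the seasonal vaccine, Section XV names one product, and nothing says that composition changed between seasons.
- **EA2 uses within-woman changes.** A constant assay offset on the analysed scale cancels if a woman's samples share a batch, and the documents give no reason for luteal hormone change to move by 0.5 to 1 SD between seasons. This stands, and it makes the larger figures unlikely. EA4's raw 24 h and 48 h levels lack that protection.
- **Assay batches.** That pilot results exist shows when the samples were first assayed. It does not show which values enter the final analysis, since re-assay is neither planned nor ruled out. The one modification that can be identified adds cytokine sampling in the non-vaccinated cycle, which EA2 and EA4 do not use.
- **EA4 may have almost no events.** At the Protocol's own myalgia/malaise rate, season is not its main difficulty. This stands.
- **Balance by prior vaccination.** The equal-numbers aim prevents bias only if it holds within each season, which is not stated.

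These parts reduce the size of the concern. They do not supply a reason to leave season out.

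**Conclusion.** The point holds as a modest, inexpensive improvement to exploratory analyses. The 90 women span two or three seasons including the pilot, the stated methods for EA2 and EA4 are unadjusted, and nothing separates seasons. That these analyses pool all women is an inference, but no passage sets the pilot aside.

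The size rests wholly on assumed season shifts. For EA2, moderate shifts give about 8% false positives in place of 5%, or power of about 0.60 to 0.74 where season adjustment gives 0.82. A reader might take the 41% as the expected error rate; it requires a full 1 SD shift in both variables, for which the documents give no evidence. A reader might also extend the concern to the primary progesterone comparison; because each woman is her own control, that comparison is largely unaffected. For EA4, the 13.5% depends on symptom rates well above the roughly 2% given for myalgia/malaise.

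**What to change.** - **EA2:** report the correlation adjusted for influenza season, as a partial correlation given season or, for Spearman, with ranks taken within season and combined.
- **Prior-vaccination comparison:** state a method, for which a linear model with prior-vaccination group and season as fixed effects would serve.
- **EA4:** use the same form of model, with symptom status and season, if enough women have symptoms. If only about two do, report EA4 descriptively by season.
- **Pilot samples:** state whether pilot values are used as first measured or re-assayed, and show EA2 with and without the pilot women.

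Season is known for every woman, so the change is wording only. It uses up to 2 degrees of freedom with three seasons, or 1 with two. With no season difference, power for a correlation of −0.30 goes from 0.83 to 0.82.

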Title: Immune response to influenza vaccination and effect on reproductive hormone

Clinicaltrials.gov ID: NCT01978262

Document Date: January 24, 2018

The power calculations are based on specific aim 1, with regards to changes in progesterone.

SA1: To determine if vaccination with IIV prior to ovulation (day 11 of menstruation) is associated with changes in post-ovulation serum reproductive (progesterone and estradiol) hormone concentrations. *-H 1: Post-vaccination serum progesterone concentrations will be lower in the month after vaccination than measured prior to vaccination.*

We are planning to study 30 adult non-pregnant women each year. Based on the results from the first 30 student enrollees, we estimate the log (base 10) mean (SD) serum concentration of progesterone during the luteal phase of menstruation prior to vaccination is 0.71 (\pm 0.51), and 0.58 (\pm 0.54) post vaccination. This difference of -0.13 on the log (base 10) scale corresponds to a median ratio of 0.74 in other words, a 26% decrease in median progesterone levels after vaccination. The observed correlation in these log concentration values was 0.60. For a total sample size of 90 women (base task order and 2 option years), assuming similar standard deviation in log (base 10) pre- and post- vaccination values as observed in the initial sample of 30, the following table shows to the power to detect a given median post-vaccination to pre-vaccination concentration ratio for several pre- and post- concentration correlation values. These results are based on a type-1 error level of .05.

	Correlation		
Median Ratio	0.55	0.60	0.65
0.75	0.63*	0.69	0.74
0.70	0.82	0.86	0.90
0.65	0.93	0.95	0.97

* values in italics give estimated power to detect the specified median ratio for a specified correlation between the pre- and post-vaccination progesterone values
